3 STUDY DESIGN

Study A: Cross-sectional cohort study

Study B: Observational longitudinal cohort study

Research Ethics Committee approval and R&I approval will be sought for the study. Participants who meet the entry criteria will be recruited and consented by the investigator, or any GCP qualified member of the local research team who has delegated responsibility for study recruitment. Participants will be recruited from King's College Hospital, Royal London Hospital outpatients and wards and nuclear medicine department. Participants will be offered a minimum of 24 hours to reflect on the patient information sheet (PIS), which will be provided during initial discussion. Participants will be selected purposively to include a range of age, gender, ethnicity (at least 50% African/Afro Caribbean), severity of renal disease and clinical settings. Participants in study A will be able to participate in study B if they wish to do so.

Demographics, Body mass index, waist circumference and lean body mass (Fresenius - Body Composition Monitor and clinician estimated), mobility at home, mode of transportation to come to hospital, length and cost of travel, carer details, drug history, number of hospital visits and GP visits per year and reason for laboratory creatinine testing (e.g. monitoring Ig A nephropathy) will be recorded. Data will be transferred following pseudo-anonymisation into a study specific database by the research team.

POC-Cr testing

Capillary POC-Creatinine concentration will be assessed by NovaMaxCreat (NovaBio) and Epoc (Siemens) POC hand-held devices. A quality control will be performed for each POC-Cr device each day by the study nurse and by participants, ensuring the reagent batch conforms the manufacturers' quality specifications. POC reagents will be stored and used following manufacturers' specifications.

Study A: POC-Cr will be assessed using the NovaMaxCreat and Epoc devices. Finger-prick capillary whole blood samples will be taken (0.05 uL for NovaMaxCreat and 0.9 uL for Epoc) using lancets by the research team. Venous serum creatinine for routine care (Isotope Dilution Mass Spectrometry (IDMS) Traceable Enzymatic assay) and ^{99m}Tc-DTPA glomerular filtration rate testing (where available) will be extracted from hospital laboratory databases. Participants not undergoing routine ^{99m}Tc-DTPA glomerular filtration rate testing will also have a 'eGFR filtration panel assessment – Beta-2-microglobulin, cystatin-C (processed by Synlab/ViaPath) and beta-trace-protein concentration (processed by Affinity laboratories), assessment on their venous blood sample.

Participants will be trained to use the POC-Cr device by the research team and time taken recorded and asked to perform one POC-Cr test.

In addition, the Epop Blood Analysis system, will also measure capillary potassium concentrations, which will be compared to serum potassium (taken from the venous blood sample for routine clinical care). This will be tested in the laboratory using the Roche Chemistry Analyser Cobas 8000.

Study B: Participants will be trained to use the POC-Cr device, NovaMaxCreat (NovaBio) by the research team and time taken recorded. Participants will be taught how to perform quality controls. All sample results will be digitally recorded by the device and downloaded after the device is returned. Participants will be asked to do one test at the hospital (with a simultaneous lab creatinine on site for validation), then to self-monitor four times per day (first thing in morning, midday, before evening meal/early evening, before bed) and each test recorded in a paper diary or electronically as desired. Details reported will include date and time of test, test success, device and non-device failures (test results, missed testing and reasons for missed test (e.g. forgot, did not want to test) and adverse events (e.g. pain or infection or prolonged injury after sampling, pre-syncopal or syncopal episode).

For participants who perform finger-prick testing for capillary blood glucose monitoring, both samples (creatinine using NovaMaxCreat and glucose using their usual device) can be taken from the same finger-prick test. However, participants will be advised to take the creatinine sample first.

Participants will also be given the option to test more frequently or for longer than one week if desired and to report the reason for additional tests (concerned about previous result, demonstration for friend or family member). Reassurance will be given to participants about possibility of abnormal results and research team contact provided for discussion and repeat testing if desired of changes in results. Participants can have the opportunity (after consent) to trial self-testing on site, and decide if they wish to participate in self-monitoring at home.

Service User Technology Acceptability Questionnaire (SUTAQ): The SUTAQ questionnaire has been developed to measure the acceptability of telehealth and remote monitoring of chronic disease and includes assessment of quality of life, well-being, psychological processes and other patient-reported outcome measures (PROMs) which are evaluated with six acceptability scales: enhanced

care, increased accessibility, privacy and discomfort, care personnel concerns, kit as substitution and satisfaction.¹⁴ We have piloted the SUTAQ with minor adaptation developed with PPIE in our outpatient department. SUTAQ answers will be collected by the research team on tablet devices for Study B. Permission has been provided to use the SUTAQ by [name].

Samples (for Study A) will be sent to:

- i) Synlab UK - King's College Hospital NHS Foundation Trust (Cystatin C, Beta-2-microglobulin)
- ii) Affinity Biomarker Labs, [name] (beta-trace-protein)

The study sites and corresponding principal investigators are included in the table below.

Site	Study A and /or B	PI
King's College Hospital	A + B	[name]
Queen Alexandra Hospital, Portsmouth	B	[name]

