2.2 Secondary Objectives

Study A

- To define a threshold of POC-Cr concentration in people of different ethnicities which are confirmatory of eGFR $<60\text{mls}/\text{min}/1.73\text{m}^2$ (Kidney Disease Improving Global Outcomes; KDIGO Definition Stage 3) and a range of POC-Cr which may require further confirmation.
- To compare capillary POC-Cr with venous serum enzymatic creatinine concentrations (serum Cr) in people of different ethnicities performed by health care professionals

Study B

- To assess test success rate, safety, training time, patient experience and acceptability of serial capillary POC-Cr testing

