8 STATISTICAL METHODS

Study A: Readings taken with measured with NovamaxCreat and Epoc blood analysis system will be analysed separately. Bland-Altman plots and Passing-Bablok regressions will be generated for POC-Cr concentrations using Stata version 21 or later. The analytical error percentage compared to the reference standards (IDMS enzymatic traceable and 99mTc-DTPA and GFR filtration panel) ($=100 \times ([\text{POC device}] - [\text{reference standard}]) / [\text{reference standard}]$) will be calculated for each POC-Cr recording in each participant. In addition, average analytical error percentage and a 95% confidence interval (95%CI) will be calculated following Clinical Laboratory Standards Institute procedures.¹⁶ Criteria used to check analytical error percentage will be derived from the 'Desirable Specifications for Allowable Total Error (ATE)' database for creatinine (ATE=8,87%)¹⁵ and from the Laboratory Working Group of the National Kidney Disease Education Program (NKDEP) for eGFR (ATE=10%)¹⁷. Although the 10% ATE for eGFR is actually a performance specification for creatinine, it has been used in as an acceptable total error for eGFR.^{18,19,20} Categorical agreement of POC-Cr concentrations with the reference standards will be calculated using the unweighted Kappa statistic. Error analysis using predefined minor and major classification errors will be performed for POC-Cr concentrations. POC-Cr concentrations and reference standards will also be assessed by Deming regression and Pearson's correlation coefficient. Bias offset required will be recorded

Proportion of patients correctly identified to have CKD $eGFR < 60 \text{mls/min/1.73m}^2$ will be reported. Sensitivity and Specificity of different Cr thresholds calculated.

Study B: Number of tests attempted per participant, daily frequency of testing and proportion of successful attempts will be reported. Reasons for unsuccessful attempts and adverse events will be described and quantified if appropriate. Time taken to train per patient will be reported in minutes as median and IQR.

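### Study B names only the participant's own diary as a source for failed home tests and plans no objective count of attempts, so the success rate is liable to bias

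*Protocol*

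**What the plan says.** Test success is part of the Study B secondary objective in Protocol section 2.2: "To assess test success rate, safety, training time, patient experience and acceptability of serial capillary POC-Cr testing". Section 8 fixes the summaries: "Number of tests attempted per participant, daily frequency of testing and proportion of successful attempts will be reported". The denominator is therefore attempts, not scheduled tests.

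Section 3 (POC-Cr testing, Study B) names two sources of data:

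- The device: "All sample results will be digitally recorded by the device and downloaded after the device is returned".
- The participant: "each test recorded in a paper diary or electronically as desired". The content of that record is also listed: "Details reported will include date and time of test, test success, device and non-device failures", together with missed tests and the reasons for them.

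The schedule asks participants, after one test in hospital, "then to self-monitor four times per day". It is not a ceiling: "Participants will also be given the option to test more frequently or for longer than one week if desired". In section 4, Table 2, test success reporting is marked for the home monitoring period only and not for the Day 8 visit. Section 3 also has participants run a daily quality control (QC) test on the device.

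**The concern.** A successful home test leaves two traces, one in the device memory and one in the diary. A failed attempt (too little blood, an error reading, a test abandoned part-way) has one named source, the diary. Nothing in the protocol checks whether the diary is complete, and the two sources are not compared when the device comes back.

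Two things are at stake. The first is the success rate itself. Section 1 treats the feasibility of self-testing, including how many tests succeed, as critical to understand, and presents this study as preliminary data for later funding. The second is the planned comparison of acceptability questionnaire scores with testing success in section 8. If a participant's apparent success depends partly on how well the diary was kept, that comparison picks up diary-keeping as well as performance.

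**Working it through.** The protocol gives no expected success rate or precision target for this endpoint, so there is no figure of its own to reproduce. The check is how far the reported rate can depart from the true one.

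**Inputs from the protocol.** Four scheduled tests a day for seven days: 4 × 7 = 28 per participant, or 28 × 40 = 1,120 for the minimum of 40 participants.

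**Inputs assumed.** True success rate per attempt *s*; share of failures entered in the diary *r*; share of successes entered in the diary *q*. The documents give none of these, so a range is shown.

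**Route 1: successes from the download, failures from the diary.** Observed rate = s / (s + (1 − s) r).

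| True rate *s* | r = 0.75 | r = 0.50 | r = 0.25 |
|---|---|---|---|
| 0.95 | 0.962 | 0.974 | 0.987 |
| 0.90 | 0.923 | 0.947 | 0.973 |
| 0.80 | 0.842 | 0.889 | 0.941 |
| 0.70 | 0.757 | 0.824 | 0.903 |

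For s = 0.85 and r = 0.50: 0.85 / (0.85 + 0.15 × 0.50) = 0.85 / 0.925 = 0.919. On this route the error can only be upward. It is about 2 points at s = 0.95 and 9 points at s = 0.80 when half the failures are missing.

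**Route 2: both from the diary.** Observed rate = s q / (s q + (1 − s) r). With s = 0.80:

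- q = 0.75, r = 0.75: 0.60 / (0.60 + 0.15) = 0.800, no bias.
- q = 0.90, r = 0.50: 0.72 / (0.72 + 0.10) = 0.878, too high.
- q = 0.50, r = 0.90: 0.40 / (0.40 + 0.18) = 0.690, too low.

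**The routes disagree on the same data.** In the last case, route 1 would give 0.80 / (0.80 + 0.20 × 0.90) = 0.816 where route 2 gives 0.690.

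**The schedule does not rescue the count.** Suppose a participant makes 24 attempts, of which 20 succeed and 4 fail. The true rate is 20/24 = 0.833. If two failures are not written down it becomes 20/22 = 0.909. Dividing by the schedule gives 20/28 = 0.714, which mixes missed tests with failed ones and is a different quantity. Attempts may also exceed 28, and a failure followed by a successful retry leaves no empty slot to show that it happened.

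**With every attempt counted** (r = 1), route 1 returns *s* exactly.

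**The case against.** A reader might infer that the success rate is biased upwards, that the error always favours the device, or that the poorest diary-keepers will look most successful. The protocol does not support that. All three need the numerator to come from the download and the failures from the diary, and section 8 names no source. Test success is itself an item the participant reports, so a diary-only rate is a possible reading, and route 2 shows that its bias can be zero, upward or downward.

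Nor does the protocol say that the device discards failed tests. It speaks of sample results and is silent on error readings. If those are stored, device failures are at least partly covered. Attempts that never register on the device would still rest on the diary.

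It can also be said that naming the source belongs in an analysis or data-management plan, that the endpoint is secondary and descriptive, and that comparing downloaded results with diary-recorded successes would show how complete each diary was. These points stand in part. The choice of source could be settled elsewhere, the endpoint does limit the weight of the point, and such a comparison would support sensitivity bounds. But it measures how completely successes were recorded, not failures. What remains concerns collection: if attempts are not counted when the device is returned, no later document can recover them.

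Finally, the supply and return of test strips is not described; the protocol refers only to reagents. A count of consumables therefore assumes that each non-QC test uses one countable item.

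**Conclusion.** The point holds as a weakness in data collection. The rate is defined per attempt, the only named source for a failed home attempt is the participant's diary, and no objective count or reconciliation is planned. The result is liable to bias: upward if successes come from the download and some failures go unrecorded, and in either direction if both come from the diary with unequal reporting. The sizes shown rest on assumed failure and reporting rates and are illustrations only. It affects a secondary, descriptive endpoint and the questionnaire comparison that uses it, not the accuracy comparisons. It is worth correcting because the remedy is cheap and has to be in place before the data are collected.

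**What to change.** 1. Record the number of test consumables issued to each participant and the number returned unused.
2. At the Day 8 visit, reconcile that count with the device download, including any stored error readings, and with the diary. State in the protocol whether the device stores failed tests.
3. Define attempts as consumables used minus QC tests, and successes as non-QC results on the device. Take the QC count from the device if it labels those tests; otherwise it rests on the participant's record, which should be acknowledged.
4. Keep extra tests in both numerator and denominator, or report them separately in both. Dropping them from one side only can give nonsense: 24 successes in 28 scheduled attempts plus 7 successful extra tests would give 31/28.
5. Use the diary for reasons and for attempts that used no consumable, and report the diary-based rate as a sensitivity figure.

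The cost is a few extra case report form fields and a short check at a visit that already takes place. The downside is that a lost or wasted consumable counts as a failed attempt, which lowers the rate slightly. In the example above, one lost item would turn 20/24 = 0.833 into 20/25 = 0.800 for that participant.

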STUDY SUMMARY

STUDY OVERVIEW	
Full title	Renal function Assessment with Point of Care creatinine In Diverse populations (RAPID)
Objectives	
Study A
 
 • To compare capillary POC-Cr with venous serum enzymatic creatinine concentrations (serum Cr) in people of different ethnicities performed by health care professionals and patients • To compare estimated glomerular filtration rate (eGFR) using POC-Cr and serum Cr with formal GFR assessment in people of different ethnicities • To define a threshold of POC-Cr concentration in different ethnicities which are confirmatory of eGFR <60mls/min/1.73m² (Kidney Disease Improving Global Outcomes; KDIGO Definition Stage 3) and a range of POC-Cr which may require further confirmation 
Study B
 
 • To conduct an observational cohort study of serial capillary self-testing POC-Cr for at least one week. • To compare single and serial capillary POC-Cr compared with single venous creatinine concentration IDMS traceable enzymatic assay • To assess test success rate, safety, training time, patient experience and acceptability of serial capillary POC-Cr testing
Type of trial	Two centre cross-sectional study and prospective longitudinal cohort study
Trial design and methods	
375 participants (including > 40 of African/African-Caribbean ancestry) having venous serum creatinine and 99mTc-DTPA nuclear medicine or venous GFR filtration panel testing will be recruited to a cross sectional study (Study A)
 
At least 40 patients with CKD will be recruited to a longitudinal study (Study B)
 
Demographics, medical and transportation details will be recorded
 
Finger-prick capillary creatinine will be assessed by POC-Cr device; Venous serum creatinine concentration (Isotope Dilution Mass Spectrometry (IDMS) Traceable Enzymatic assay).
 
Participants will be trained to use POC-Cr device, asked to self-monitor up to four times per day and report details including test failure and adverse events.
 
Patient experience and acceptability will be assessed using Service User Technology Acceptability Questionnaire.

Health condition(s) or problem(s) studied	Chronic Kidney Disease
Target sample size	At least patients 415 (Study A: 375; Study B: At least 40)
Trial duration per participant:	Study A: 1 Day Study B: 1 week

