4 STUDY SCHEDULE

Enrolment process:

Study A: Participants will be identified through database screening (Renalware and PIMS/Electronic Patient Records) and approached in outpatient or wards by research specific staff and provided with a patient information sheet (PIS).

Study B: Participants will be identified and approached in outpatients by clinical staff and provided with a patient information sheet (PIS).

Participants who meet the inclusion and exclusion criteria for the study will not require any further screening prior to involvement in the study. Participant will provide written consent and samples taken for analysis.

Follow up: None, unless required following an Adverse Event. In such cases, the follow up will be as determined by the Principal Investigator.

Participant withdrawal criteria and procedures: If a participant wishes to withdraw their consent their information will be destroyed.

End of the study: The end of the study will occur after the final patient is recruited and final sample collection.

Table 1: Study A - Schedule of Assessments

	Pre Screening	Study Visit
Visit No		1
Informed Consent		X
Medical History		X
Vital Signs and lean body mass Bioimpedence		X
Eligibility confirmation	X	X
Concomitant Medication Review		X
Venous Serum Creatinine		X
POC-Cr		X
99mTc-DTPA		±2 days of POC-Cr
Or Biomarker panel		X
Adverse Events Review		X

Table 2: Study B - Schedule of Assessments

	Pre Screening	Baseline	Home Monitoring	Final Visit
Visit No		Day 1		Day 8
Window of flexibility for timing of visits:				Day 7-10
Informed Consent		X		
Medical History		X		
Vital Signs		X		
Eligibility confirmation	X	X		
Concomitant Medication Review		X		X
Venous Serum Creatinine		X		X
POC-Cr Health Care Professional		X		X
POC-Cr Patient		X	X	X
Test success reporting			X	
Adverse Events Review		X	X	X
SUTAQ Questionnaire				X

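### Study B schedules its acceptability questionnaire only at the final visit, so SUTAQ results will describe only participants who reach that visit and will probably, though not certainly, look too favourable

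*Protocol*

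**What the plan says.** Section 2.2 makes acceptability a secondary objective of Study B: "To assess test success rate, safety, training time, patient experience and acceptability of serial capillary POC-Cr testing". The Study Summary names the SUTAQ as the instrument for patient experience and acceptability, and gives a recruitment target of at least 40 for Study B.

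Section 3 lets participants make the decision about home testing after they have consented: "Participants can have the opportunity (after consent) to trial self-testing on site, and decide if they wish to participate in self-monitoring at home". On the questionnaire it says "SUTAQ answers will be collected by the research team on tablet devices for Study B", without a time point. The time point is in Table 2 of section 4. The row "SUTAQ Questionnaire" has a single mark, in the Final Visit column (Day 8, window Day 7-10), and none under Baseline or Home Monitoring.

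Section 4 also says "Follow up: None, unless required following an Adverse Event", and, for withdrawal of consent, "If a participant wishes to withdraw their consent their information will be destroyed".

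Section 8 will report SUTAQ scale scores, how the scales relate to each other, and how they relate to demographics and to the frequency, success and accuracy of testing.

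**The concern.** The protocol foresees people who consent, try the device and then say no to using it at home. Any home-monitoring study will also have some participants who leave early. For both groups the refusal or departure is itself information about acceptability, yet the schedule gives them no occasion to be asked. Two of the SUTAQ scales listed in section 3 cover privacy and discomfort, and satisfaction. These are the scales on which such people would most plausibly differ from completers.

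The protocol gives its own reasons to care. Section 1 warns that self-monitoring may raise anxiety and treats understanding of patient experience as essential. Section 9 records a worry among engagement participants that home monitoring could be a form of surveillance. The results are meant to support a later community screening and monitoring programme, so a selected picture of acceptability would carry forward into its design. The planned comparison of SUTAQ scores with testing frequency and success would also lack those who left before the final visit.

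A statistical analysis plan cannot repair this, because it cannot recover questionnaires that were never given.

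**Working it through.** **Who is asked under the schedule as written**

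| Participant | SUTAQ scheduled? | Basis |
|---|---|---|
| Completes home testing, attends Day 7-10 | Yes | Table 2 |
| Stops home testing, still attends Day 7-10 | Yes | Table 2 does not make the visit conditional on completing the tests |
| Starts home testing, leaves before Day 7-10 | No | No earlier mark in Table 2; no follow-up except after an adverse event |
| Tries the device on site, declines home testing | Not provided for | Section 3 allows it; their status and later attendance are not defined |

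The gap therefore covers those who leave before the final visit, and decliners unless they happen to be brought back for it.

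**Other data on unwillingness to test.** Section 3 has home testers record "reasons for missed test (e.g. forgot, did not want to test", as examples of why a test was missed. Section 8 reports attempts, daily frequency and reasons for unsuccessful attempts. These describe people who began home testing, and they are not SUTAQ scores.

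**Size.** The plan gives no figure to reproduce: no expected uptake, no expected drop-out, and no definition of a participant who finds testing acceptable. What follows is an illustration that uses a yes/no summary the plan does not itself define.

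Input from the protocol: N = 40, the minimum for Study B. Assumed inputs, not in the protocol: share not asked, d, from 10% to 40%; favourable share among those asked, p_c = 90%; favourable share among those not asked, p_n, from 30% to 90%.

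Value over all participants = (1 − d) × p_c + d × p_n. Overstatement = d × (p_c − p_n).

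| Not asked (of 40) | p_n = 90% | p_n = 70% | p_n = 50% | p_n = 30% |
|---|---|---|---|---|
| 4 (10%) | 90% | 88% | 86% | 84% |
| 8 (20%) | 90% | 86% | 82% | 78% |
| 12 (30%) | 90% | 84% | 78% | 72% |
| 16 (40%) | 90% | 82% | 74% | 66% |

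Against 90% among those asked, the overstatement runs from 0 points (both groups alike) to 0.4 × (0.9 − 0.3) = 24 points.

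**Bounds with no assumption about those not asked.** Take 8 of 40 not asked and 29 of the remaining 32 favourable:

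- observed: 29/32 = 90.6%
- none of the 8 favourable: 29/40 = 72.5%
- all 8 favourable: (29 + 8)/40 = 37/40 = 92.5%

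The upper bound lies above the observed value, so arithmetic alone does not settle the direction.

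**The case against.** The strongest defence is that the objective concerns serial testing and the SUTAQ measures acceptability of remote monitoring. Someone who did one supervised test has no experience of either, so asking after a week of use is a reasonable choice. This stands for the full SUTAQ in on-site decliners, several of whose items would not apply. It does not cover people who stop or leave during the home week, and it does not justify collecting nothing from decliners.

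A reader might infer that everyone who stops before Day 8 is never asked. The documents do not support that. The Day 7-10 visit also carries venous creatinine, a test by a health care professional and adverse event review, so someone who stopped testing on Day 3 could attend and be given the questionnaire. For the same reason infrequent testers are not all lost from the comparison of SUTAQ scores with testing frequency.

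A reader might also infer that decliners form a retained but unmeasured group. Section 3 does not define their status. Section 6.1 requires willingness to complete all study procedures, so a site might treat a decliner as ineligible or withdrawn. That ambiguity leaves the gap in place, since on no reading is an assessment scheduled for them.

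Finally, counts of decliners and completers are participant-flow reporting, commonly left to an analysis plan. Their absence from section 8 is not counted as an error here. They appear below only because uptake is itself an acceptability result.

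**Conclusion.** The point holds as a gap in data collection. Following the protocol as written yields SUTAQ data only from participants who reach the final visit, and nothing in the document provides an acceptability assessment for those who decline home testing or leave earlier.

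It is tempting to say that acceptability will be overstated by a given number of percentage points. That is not supported. Overstatement is the likely direction, on the assumption that people who decline or leave are less favourable than those who stay, but it is not shown. The plan reports scale scores rather than a proportion, and every rate used above other than the 40 participants is assumed. Under those assumptions the overstatement ranges from 0 to 24 points, and the present schedule would not allow the investigators to tell where in that range they are.

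For a secondary objective in a cohort of about 40 this is an inexpensive improvement worth making. It does not threaten the study's accuracy comparisons.

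**What to change.** In Table 2, schedule the SUTAQ at the Final Visit or when a participant stops home testing early, whichever comes first. At the baseline visit, add a short optional exit item for those who decline home testing after the on-site trial, covering main reason, discomfort and privacy. It should be optional because section 5 lets participants leave without giving a reason.

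In section 8, report the numbers trained, declining, starting and completing home testing as acceptability results over all consented and trained participants. Tabulate decliners' responses separately from the SUTAQ scale scores.

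Cost: one change to the schedule, one short item and a sentence or two in section 8, with no new visit and a few extra minutes of data collection. The drawback is that decliners' responses cannot be pooled with SUTAQ scores, so they qualify the main result and do not adjust it.
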